CLINICAL PROTOCOL

CTIX-KEV-201

A Phase 2 study of Kevetrin (thioureidobutyronitrile) in Subjects with Platinum-Resistant/Refractory Ovarian Cancer

Document type:	Clinical Protocol
Version number:	1.0
Version date:	08 December 2016
NCT:	NCT03042702

CONFIDENTIALITY STATEMENT

The information provided in this document is strictly confidential. This information may not be used, published or disclosed without prior written approval from Cellceutix.

PROTOCOL SYNOPSIS

Name of Sponsor/Company: Cellceutix Corporation
Name of Finished Product: Kevetrin
Name of Active Ingredient: Thioureidobutyronitrile
Title of Study: A Phase 2 study of Kevetrin (thioureidobutyronitrile) in Subjects with Platinum-Resistant/Refractory Ovarian Cancer
Study Centers: Approximately 3 sites in the United States
Number of Subjects Planned: Approximately 10 study participants with platinum-resistant/refractory ovarian cancer
Study Duration per subject: Approximately 10 weeks: 4 weeks for screening, a 3-week Kevetrin cycle, followed by a 3-week follow-up
Phase of Development: Phase 2
Primary Objective(s): 
• To evaluate safety and tolerability of two different treatment regimens of Kevetrin when administered to subjects with platinum-resistant/refractory ovarian cancer• To evaluate changes in biomarkers and molecular signatures related to cell proliferation and cell death from tumor tissue, ascites fluid, and peripheral blood after treatment with Kevetrin to subjects with platinum-resistant/refractory ovarian cancer
Secondary Objectives: 
• To evaluate the objective tumor response to treatment with Kevetrin when administered to subjects with platinum-resistant/refractory ovarian cancer• To evaluate the pharmacokinetics of Kevetrin after administration to subjects with platinum-resistant/refractory ovarian cancer
Design and Methodology: This is an open label, dose-escalation trial to study the safety, biomarker changes (including modulation of p53), objective tumor response changes, and pharmacokinetics following administration of two different treatment regimens of Kevetrin over a 3-week period to subjects with platinum-resistant/refractory ovarian cancer. Following the 3 weeks of Kevetrin dosing, subjects are to be followed up for 3 weeks after completion of Kevetrin treatment. Standard of care treatment, as medically appropriate and per local

guidelines, outside of this study protocol can commence after the collection of the post-Kevetrin treatment biomarker samples (collected on Day 21±1 day).

The patient population recruited into this study includes those ovarian cancer patients that have platinum resistant/refractory disease, defined as disease progression/relapse within 6 months following the last administered dose of platinum therapy (resistant), or lack of response or disease progression while receiving the most recent platinum based therapy (refractory), respectively. Patients may or may not have had additional treatment (e.g., Doxil) prior to entry in this study.

A total of approximately 10 study participants are planned to be enrolled in two cohorts of approximately 5 subjects per cohort, with enrollment in a sequential, dose-escalating fashion. Investigators and subjects will be aware of the treatment cohort into which they are recruiting. Cohort details and the planned doses are listed below:

Cohort 1 (n=5) Kevetrin Cycle

Kevetrin 250 mg/m² IV per dose every other day (q.o.d.)/ 3 doses per week (750 mg/m² per week), for 3 weeks (single cycle; total 9 doses)

Follow-up

For 3 weeks after Kevetrin treatment ends

Cohort 2 (n=5) Kevetrin Cycle

[figure not shown]
Kevetrin 350 mg/m² IV per dose every other day (q.o.d.)/ 3 doses per week (1050 mg/m² per week), for 3 weeks (single cycle; total 9 doses)

Follow-up

For 3 weeks after Kevetrin treatment ends

Cohorts 1 and 2 will be conducted in a sequential fashion, with safety data from cohort 1 evaluated by an independent Data Monitoring Committee (DMC). The DMC will make appropriate recommendations based on the available safety data as regards the intent of progressing to the higher dose cohort 2.

Study Design Schematic

If 2 of the 5 subjects in cohort 1 experience a dose-limiting toxicity (DLT) adverse event, the DMC will consider reducing the Kevetrin dose regimen for cohort 2 by 25%.

Dependent on the DLT adverse events experienced, the dose in cohort 1 may be repeated, or reduced. If no new or unexpected safety concerns are identified by the DMC safety review, enrollment of subjects to cohort 2 with a higher dose regimen of Kevetrin will commence.

If a subject experiences a DLT adverse event during treatment with Kevetrin, treatment with Kevetrin will be stopped and the subject will be appropriately followed-up to document the course of the abnormality until returned to a normal or baseline level, or until the adverse event/abnormality is deemed clinically stable. For any DLT adverse event, the Investigator must immediately notify the Medical Monitor by telephone and follow-up in writing.

For this study, a DLT adverse event is defined as follows, according to the NCI Common Terminology Criteria for Adverse Events (CTCAE) version 4.03:

Hematologic toxicity:

- Grade 3 or 4 febrile neutropenia or Grade 4 neutrophil count decreased of ≥ 7 days' duration
- Grade 4 thrombocytopenia or grade 3 thrombocytopenia complicated by hemorrhage

Nonhematologic toxicity:

- Any grade ≥ 3 nonhematologic toxicity unless there is clear alternative evidence that the adverse event was not caused by Kevetrin
- Grade 3 diarrhea, nausea, or vomiting may be excluded from DLT classification provided that the maximum time limit for supportive measures is 48 hours

A subject studied under this clinical protocol will commence with a screening period of up to 4 weeks, a treatment cycle with Kevetrin (3 weeks), followed by a 3-week follow-up.

Safety and tolerability will be assessed by ascertainment of AEs, physical examinations, and results of clinical laboratory testing, and vital signs assessments. Tumor measurement assessments, by computed tomography (CT) scan, will be taken pre- and post-Kevetrin treatment. Tumor biopsies and ascites fluid (if available), and blood samples for biomarkers will also be collected pre- and post-Kevetrin treatment. Serial blood samples for determination of plasma Kevetrin concentrations will be collected on Study Days 1 and 5, from 2 hours pre-infusion out to 24 hours post-infusion completion.

Any discontinuation of study treatment (Kevetrin) is to be reported by the Investigator to the Medical Monitor. Any subject that discontinues study treatment is to be followed up for (approximately) 3 weeks after the end of treatment. Subjects who withdraw from the study or discontinue treatment for reasons other than a demonstrated intolerance to Kevetrin or a DLT may trigger additional subjects to be enrolled, to obtain 5 completed subjects in each cohort.

Inclusion Criteria:

1. Evidence of a personally signed and dated written informed consent to participate in the clinical study
2. Non-pregnant female adults at least 18 years of age at time of informed consent

3. Histologically confirmed serous epithelial ovarian cancer with peritoneal metastases
4. Platinum resistant/refractory disease, defined as disease progression/relapse within 6 months following the last administered dose of platinum therapy (resistant), or lack of response or disease progression while receiving the most recent platinum based therapy (refractory), respectively
5. Measurable disease, as determined by radiologist evaluator, with at least 1 unidimensional measurable lesion (target lesion) by RECIST v.1.1 that has not previously been irradiated or biopsied
6. Presence of non-target lesions that have not previously been irradiated or biopsied; to allow for collection of needle-biopsies at Screening and after completion of Kevetrin treatment
7. Eastern Cooperative Oncology Group (ECOG) performance status of 0 or 1
8. Adequate hematologic and organ function as confirmed by laboratory values at Screening:
 - a. Bone marrow function: Absolute neutrophil count (ANC) \geq 1500 cells/ μ L (with no evidence that this ANC was induced or supported by granulocyte colony stimulating factors)
 - b. Hemoglobin \geq 9 g/dL (with no RBC transfusions within 7 days of Screening)
 - c. Platelets \geq 100,000 cells/ μ L (with no evidence that this platelet count was induced or supported by a platelet-stimulating agent)
 - d. Renal function: creatinine \leq 1.5 x ULN
 - e. Hepatic function: total bilirubin \leq 1.5 x ULN; ALT and AST \leq 3 x ULN; alkaline phosphatase \leq 2.5 x ULN
 - f. Neurologic function: neuropathy (sensory and motor) \leq CTCAE Grade 1
 - g. Coagulation status: prothrombin time (PT) \leq 1.5 ULN or INR within normal limits; and partial thromboplastin time (PTT) \leq 1.2 x ULN
9. Women of child-bearing potential are required to use effective contraception throughout the study period. Effective contraception methods include:
 - a. Total abstinence (if this is the usual lifestyle of the subject). Periodic abstinence (e.g., calendar, ovulation, symptothermal, post-ovulation methods) and withdrawal are not acceptable methods of contraception. (Subject must agree to use contraception should they become sexually active while on the study.)
 - b. Surgical sterilization (hysterectomy and/or bilateral oophorectomy) or tubal ligation at least six weeks before start of study treatment.
 - c. Male partner sterilization, occurring at least 6 months prior to screening. For female subjects on the study, the vasectomized male partner should be their sole partner.

- d. Double barrier method: Condom or Occlusive cap (diaphragm or cervical/vault caps) with spermicidal foam/gel/film/cream/vaginal suppository.
- e. Oral*/ injected/ implanted/ transdermal hormonal contraception or other forms of hormonal contraception that have comparable efficacy (failure rate <1%), e.g., hormone vaginal ring.
- f. Intrauterine device or intrauterine system.

*Stable oral contraception use (on the same pill) for a minimum of 3 months before taking study treatment.

Women are considered post-menopausal and not of child-bearing potential if they have had 12 consecutive months of natural (spontaneous) amenorrhea with an appropriate clinical profile (e.g., age appropriate, history of vasomotor symptoms) or have had surgical hysterectomy and/or bilateral oophorectomy or tubal ligation at least six weeks ago.

- 10. Estimated life expectancy of at least 6 months, in the Investigator's opinion
- 11. Willing and able to comply with scheduled visits, study assessments and laboratory tests, and other study procedures

Exclusion Criteria:

- 1. Unwilling to allow removal of tumor biological samples for analysis, i.e., biopsies of tumor lesions, and/or collection of ascites fluid from abdominal ascites (if present)
- 2. Non epithelial tumor, including malignant mixed Müllerian tumors without high grade serous component, or ovarian tumors with low malignant potential (i.e., borderline tumors)
- 3. Known presence of central nervous system metastases
- 4. Presence of tumor metastases causing significant pleural disease/effusion unilaterally or bilaterally (significant pleural effusion is defined by need for thoracentesis more frequently than once every 21 days)
- 5. Presence of ascites that requires paracentesis more frequently than once every 21 days.
- 6. A history of another primary cancer that has been active or treated within the past 3 years prior to start of study treatment, with the exception of adequately treated/resected: basal cell or squamous cell skin carcinoma or actinic keratoses; or carcinoma in situ of the breast or of the cervix; or non-invasive malignant colon polyps
- 7. Persistent toxic effects with severity of CTCAE grade 2 or greater (excluding alopecia) caused by previous treatment
- 8. History of arterial or deep venous thromboembolism within the 12 months prior to enrollment
- 9. Clinically significant cardiac disease, including:

- a. Myocardial infarction or unstable angina < 6 months prior to enrollment
 - b. New York Heart Association (NYHA) Grade II or greater congestive heart failure
 - c. Cardiac arrhythmia requiring medication (does not include asymptomatic atrial fibrillation with controlled ventricular rate)
10. Electrocardiogram (ECG) obtained at Screening which shows QTc prolongation or other medically relevant abnormalities which may affect subject safety or interpretation of study results
 11. At a higher than average risk, in the Investigator's opinion, of bowel perforation (e.g., symptoms of partial or complete bowel obstruction, recent (within 6 months) history of fistula or bowel perforation, requirement for total parenteral nutrition and continuous hydration)
 12. Active or chronic recurrent systemic infections that require continuous antimicrobial therapy during the Kevetrin study period
 13. Past medical history of infection with HIV, hepatitis B or hepatitis C
 14. Ongoing or recent history of any other uncontrolled and/or clinically significant systemic disease or condition which, in the Investigator's medical opinion, should exclude participation in the study
 15. Less than 3 weeks between major surgery and planned start of study treatment; major incisions must have healed
 16. Less than 4 weeks since last treatment for ovarian cancer
 17. Any investigational or experimental therapy or procedure or participation in any interventional trial within 4 weeks or 5 half-lives (whichever is longer) prior to start of study treatment
 18. Women of child-bearing potential who are pregnant or nursing (lactating)
 19. Previous participation in a clinical study of Kevetrin
 20. History of alcohol or substance abuse, unless in full remission for more than 6 months prior to start of study treatment
 21. Any other severe acute or chronic medical or psychiatric condition or test abnormality(ies) that, in the Investigator's opinion, puts the subject at significant risk, could confound the study results, or may interfere significantly with the subject's participation in the study

Test Product, Dose, and Mode of Administration:

Kevetrin (thioureidobutyronitrile) will be supplied by the Sponsor in 5 mL glass vials, with each vial containing 200 mg Kevetrin (lyophilized).

Kevetrin will be reconstituted in water for injection (WFI) and placed in a non-PVC infusion bag containing 250mL of 0.9% Sodium Chloride Injection USP (Braun L8002 or equivalent, provided by the site). A low sorbing (PVC-free) IV infusion set equipped with an in-line

0.2- μm pore size filter (CareFusion / Alaris 11532269 or equivalent, provided by the site) will be attached to the non-PVC bag.

Cohort 1: Kevetrin 250 mg/m² IV per dose every other day (q.o.d.)/ 3 doses per week (750 mg/m² per week), for 3 weeks

Cohort 2: Kevetrin 350 mg/m² IV per dose every other day (q.o.d.)/ 3 doses per week (1050 mg/m² per week), for 3 weeks

Nine (9) doses of Kevetrin are to be divided and administered every other day (q.o.d.) as three doses split over each 7-day period, for a single (21-day) treatment cycle.

Doses 1, 2, and 3 are each separated by approximately 48 hours; Dose 4 is administered approximately 72 hours after Dose 3. Doses 5 and 6, and doses 8 and 9 are administered approximately 48 hours after doses 4 and 7, respectively. The separation between doses 6 and 7 is approximately 72 hours.

Each Kevetrin dose is to be administered intravenously over a duration of no less than 180 minutes (3 hours). A pre-medication regimen is recommended for administration within 30 to 60 minutes prior to initiation of each Kevetrin infusion.

Data Analysis:

Details of the statistical methodology for summary and analyses of the data collected in this study will be prepared separately from this protocol in a statistical analysis plan (SAP).

All statistical analyses will be performed using SAS version 9.3 or higher.

Safety endpoints: AEs, SAEs, dosing compliance, any discontinuations from Kevetrin treatment due to toxicities, and changes in laboratory values, vital signs, ECGs, and ECOG performance status, and incidence of clinical laboratory, blood pressure, heart rate, temperature and respiration rate, and ECG abnormalities.

Biomarker endpoints:

- Change from baseline in tumor tissue markers and/or cellular markers (in cells separated from ascites fluid) including, but not limited to, changes in transcriptional and translational pathways leading to anticancer activity such as p53 signaling pathway, miRNA-34a, and other tumor activity markers.
- Change from baseline in ascites fluid markers and/or plasma markers, including CA-125, CCL2, miRNA-25, miRNA-27a, and miRNA-1274b.

Tumor measurement endpoints:

- Number of subjects in each RECIST response category (complete response, partial response, stable disease or progressive disease)
- Number of subjects with confirmed objective tumor response according to RECIST
- Change from baseline in tumor size (defined as sum of the longest diameters as measured among all target lesions)

All safety data, demographic and baseline characteristics, will be summarized descriptively through appropriate data tabulations, descriptive statistics, and categorical summaries.

Biomarker and tumor measurement endpoints will be summarized with descriptive statistics by cohort and visit. Summary statistics for continuous variables will include N, mean, standard deviation, minimum, median, maximum. Summary statistics for discrete variables will be presented in contingency tables and will include absolute and relative frequencies.

Pharmacokinetic parameters will be estimated from those subjects with a sufficient number of plasma concentrations to allow for such estimation.

Interim analyses may be conducted to support decision making concerning the current clinical study, the Sponsor's clinical development projects in general or in case of any safety concerns. As this is an open label study, safety and efficacy data (individual and aggregate) will be reviewed by the Sponsor on an ongoing basis throughout the study.

A planned interim analyses for investigating safety will be conducted after completion of cohort 1. Safety data will be provided to an independent DMC for review. The DMC will make appropriate recommendations based on the available safety data as regards the intent of progressing to the higher dose cohort 2. A full review by the Sponsor of all data from participants in cohort 1 after cohort completion will also be conducted.

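### Does the plan need its own biomarker sampling and analysis rule for subjects who stop Kevetrin early?

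*Combined protocol and SAP*

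**What the plan says.** All the relevant text is in the Protocol Synopsis.

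- **Sampling day.** Design and Methodology allows standard care outside the protocol to begin once the closing biomarker collection is done, and dates that collection: "post-Kevetrin treatment biomarker samples (collected on Day 21±1 day". The sentence just before it describes a full course: "Following the 3 weeks of Kevetrin dosing, subjects are to be followed up for 3 weeks after completion of Kevetrin treatment".
- **Other references to sampling.** Later in the same section, "blood samples for biomarkers will also be collected pre- and post-Kevetrin treatment". Inclusion criterion 6 requires suitable lesions "to allow for collection of needle-biopsies at Screening and after completion of Kevetrin treatment". Neither gives a day.
- **Early stopping.** A DLT ends Kevetrin treatment. "Any subject that discontinues study treatment is to be followed up for (approximately) 3 weeks after the end of treatment". Biomarker samples are not mentioned there.
- **Replacement.** Withdrawals or stops "for reasons other than a demonstrated intolerance to Kevetrin or a DLT may trigger additional subjects to be enrolled", the aim being five completed subjects per cohort.
- **Dosing calendar.** Test Product, Dose, and Mode of Administration gives the spacing of the nine doses: "Doses 1, 2, and 3 are each separated by approximately 48 hours; Dose 4 is administered approximately 72 hours after Dose 3", with the same pattern in the following weeks.
- **Analysis.** Data Analysis plans N, mean, SD, minimum, median and maximum for the biomarkers, per cohort at each visit. It leaves the detailed methodology to a separate SAP, whose text is not among the documents reviewed.

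**The concern.** Biomarker change is one of two primary objectives, and each cohort has about five subjects, so one value is 20% of a cohort summary. The only dated reference to the closing sample follows a sentence about three full weeks of dosing, so it can be read as describing completers only. On that reading, a site with an early stopper could sample her on Day 21, when she stops, or not at all, and each choice could be called post-treatment.

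The summary could then combine samples taken shortly after the last infusion with samples taken up to three weeks after it, in subjects who also received fewer doses. Subjects who stop for a DLT or intolerance fall outside the replacement provision, so biomarker data lost with them would not be made up. Because the start of standard care is tied to the same sample, its timing for an early stopper also looks unsettled.

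**Working it through.** **1. Dosing calendar.** Put dose 1 on Day 1 and apply the stated gaps of 2, 2, 3, 2, 2, 3, 2 and 2 days (48 or 72 hours). The doses fall on Days 1, 3, 5, 8, 10, 12, 15, 17 and 19. This agrees with the nine-dose, 21-day cycle. It also agrees with the PK days, which are Days 1 and 5 and so coincide with doses 1 and 3: "Serial blood samples for determination of plasma Kevetrin concentrations will be collected on Study Days 1 and 5".

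**2. Lag from last dose to sample if Day 21±1 applies to everyone.** Lag = (20 − last dose day) to (22 − last dose day). End of follow-up = last dose day + 21.

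| Last dose | Study day | Lag (days) | Follow-up ends about Day |
|---|---|---|---|
| 1 | 1 | 19–21 | 22 |
| 2 | 3 | 17–19 | 24 |
| 3 | 5 | 15–17 | 26 |
| 4 | 8 | 12–14 | 29 |
| 5 | 10 | 10–12 | 31 |
| 6 | 12 | 8–10 | 33 |
| 7 | 15 | 5–7 | 36 |
| 8 | 17 | 3–5 | 38 |
| 9 | 19 | 1–3 | 40 |

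The third column shows why the point attracts attention. The last column answers part of it: follow-up reaches the sampling window (Days 20 to 22) in every row, including a stop after one dose. The fixed day can therefore be met by any treated subject who remains in follow-up, and the sampling sentence does not contradict the early-discontinuation sentence.

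**3. How often it could arise.** The documents give no stopping rate. If each subject had a 10%, 20% or 30% chance of stopping early for toxicity (assumed), the chance of at least one such subject among five is 1 − (1 − p)^5 = 0.410, 0.672 or 0.832. These figures show how small the cohorts are; they do not predict what this trial will see.

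**4. Precision.** Suppose two of five subjects had a DLT before dose 9 and only completers were summarized. The 95% half-width for a mean change, t(0.975, n−1)/√n, would go from 2.776/√5 = 1.24 SD to 4.303/√3 = 2.48 SD. But Data Analysis plans no confidence interval and no completers-only summary. If the early stoppers are sampled on Day 21±1, n can stay at five. The doubling therefore describes no output of the plan.

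**5. Bias.** The documents give no time course for any marker, and early stoppers differ from completers in exposure as well as in sampling lag. Neither the direction nor the size of any distortion can be derived.

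**The case for a change.** The strongest case for a change is that the lag difference is real even on the uniform reading: 1 to 3 days for completers against as much as 21 days for an early stopper. A day that can be met is not the same as a comparable measurement. The synopsis does give an evaluability condition for PK parameters and gives none for biomarkers, although biomarkers rank higher among the objectives. The sponsor also reviews open-label data throughout, so a rule settled after cohort 1 biomarker data have been seen could be chosen with knowledge of the values.

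Part of this stands. The text has no sampling day specific to early stoppers, no biomarker analysis set, and no statement on whether replaced subjects remain in the summary. How the standard-care sentence is meant to work for an early stopper is for the sponsor to confirm; no clinical rule is proposed here.

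It does not carry through to a change, for three reasons. First, the available text is a synopsis without a schedule of assessments, and it expressly sends statistical methods to another document, so silence here is weak evidence that no rule exists. Second, no hypothesis is tested on the biomarkers, so neither type I error nor power is at risk. Third, two parallel summaries of about five subjects, differing by perhaps one or two, would add little to an individual listing. Non-replacement after a DLT or intolerance is defensible because those subjects are informative for the other primary objective, safety and tolerability.

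**Conclusion.** No change to the plan follows. This is a gap in detail that analysts fill sensibly, not a contradiction or a wrong rule. One sampling day is stated without exception, and it lies within follow-up for a stop after any dose. If it is applied to all, early stoppers are sampled 3 to 21 days after their last dose, against 1 to 3 days for completers. With so few subjects, that difference can be read directly from a listing of doses received and days since last dose.

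The conclusion rests on two assumptions: that Day 21±1 means what it says for every treated subject, and that the separate SAP defines who is summarized, as such documents normally do. If the sponsor intended the day for completers only, a clarifying sentence would be useful, but no stated analysis or result would have to be corrected.

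### Once cohort 2, or a repeated or reduced-dose cohort, is open, the supplied synopsis requires no enrollment hold or DMC review at any DLT count

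*Combined protocol and SAP*

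**What the plan says.** Design and Methodology, in the Protocol Synopsis, plans two sequential cohorts of about five subjects, at 250 and then 350 mg/m² per dose. The DMC evaluates the cohort 1 safety data before cohort 2 opens. The only DLT count follows the Study Design Schematic heading: "If 2 of the 5 subjects in cohort 1 experience a dose-limiting toxicity (DLT) adverse event, the DMC will consider reducing the Kevetrin dose regimen". The reduction named is 25%, and it applies to cohort 2. The same paragraphs add "Dependent on the DLT adverse events experienced, the dose in cohort 1 may be repeated, or reduced". If the DMC review finds nothing new or unexpected, "enrollment of subjects to cohort 2 with a higher dose regimen of Kevetrin will commence".

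Two provisions apply to any subject in any cohort. After a DLT, "treatment with Kevetrin will be stopped and the subject will be appropriately followed-up". In addition, "For any DLT adverse event, the Investigator must immediately notify the Medical Monitor by telephone and follow-up in writing".

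Data Analysis states that "A planned interim analyses for investigating safety will be conducted after completion of cohort 1", and that the DMC makes "recommendations based on the available safety data as regards the intent of progressing to the higher dose cohort 2". The Sponsor's scheduled full data review is also for cohort 1. Beyond that, the Sponsor reviews safety and efficacy data continuously. Further interim analyses are permitted, including for a safety concern, but are not required.

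**The concern.** The count, the DMC's task and the planned interim all serve the decision to leave cohort 1. Nothing separate covers entry within the cohort that follows. Cohort 2 is planned at the highest dose in the trial. If its first two subjects both had DLTs, the synopsis would leave two matters to discretion: whether the remaining subjects start, and whether anyone independent of the Sponsor looks at the data. Subjects not yet started, and those still in their three-week cycle, carry that risk. Safety and tolerability of both regimens is a primary objective, yet required independent review is tied to the lower-dose cohort.

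**Working it through.** **Step 1: what each safeguard requires once a later cohort is open.**

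| Provision (synopsis section) | Applies to | DLT count | Hold on entry required | DMC review required |
|---|---|---|---|---|
| 2-of-5 rule (Design and Methodology) | Cohort 1 | 2 of 5 | No; DMC considers a lower cohort 2 dose | Yes, at the end of cohort 1 |
| DMC remit (Design and Methodology; Data Analysis) | Cohort 1 data; opening cohort 2 | None | Gate between cohorts | Yes, at the gate |
| Planned safety interim (Data Analysis) | After cohort 1 | None | No | Yes, at the gate |
| Subject-level DLT stop (Design and Methodology) | Any subject | One, own DLT | No | No |
| Medical Monitor notice (Design and Methodology) | Any subject | Each DLT | No | No |
| Ongoing Sponsor review (Data Analysis) | Whole study | None | No | No |
| Optional interim analyses (Data Analysis) | Whole study | None | No | No |

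Only the last four rows operate after cohort 2 opens. The required cohort-level response is therefore the same, namely none, for 0 to 5 DLTs in five subjects.

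**Step 2: what a two-DLT rule would do in one later cohort.** The plan gives no operating characteristic to reproduce.

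Inputs:
- From the synopsis: five subjects per cohort; doses of 250 and 350 mg/m², so 350/250 = 1.40.
- Assumed, because the synopsis gives neither: the true DLT rate p, and how far apart subjects start. Subjects are treated as independent and exactly five start; replacements are ignored.

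Let A(k) be the chance of at least two DLTs among the first k subjects:

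A(k) = 1 − (1−p)^k − k·p·(1−p)^(k−1)

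For p = 0.10, A(5) = 1 − 0.59049 − 0.32805 = 0.081. For p = 0.20, A(5) = 1 − 0.32768 − 0.40960 = 0.263.

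| p | A(2) | A(3) | A(4) | A(5) |
|---|---|---|---|---|
| 0.10 | 0.010 | 0.028 | 0.052 | 0.081 |
| 0.20 | 0.040 | 0.104 | 0.181 | 0.263 |

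- **Review triggered:** A(5), about 8% and 26%.
- **Entry actually held:** at most A(4), about 5% and 18%. This bound is reached only if each subject's DLT status is known before the next starts (full stagger).
- **Mean subjects spared, full stagger:** A(2) + A(3) + A(4) = 0.010 + 0.028 + 0.052 = 0.09 at 10%, and 0.040 + 0.104 + 0.181 = 0.32 at 20% (0.3248 before rounding).
- **Mean spared, one-subject overlap** (each subject starts while only the previous one is under observation): A(2) + A(3) = 0.04 and 0.14.
- **Mean spared if all five have started:** 0 at any rate.

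At higher assumed rates of 30%, 40%, 50% and 60%, A(5) is 0.47, 0.66, 0.81 and 0.91. Mean subjects spared are 0.65, 1.04, 1.44 and 1.83 with full stagger, and 0.31, 0.51, 0.75 and 1.01 with one-subject overlap.

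**The case against.** **Only the synopsis is available.** The protocol body and DMC charter are not supplied, the SAP is prepared separately, and a figure is not shown. A synopsis need not carry every operational rule. A reader might infer that the trial has no such rule anywhere; the documents do not support that. This objection stands: it limits the point to the synopsis and makes checking the other documents the first action.

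**Cohort 2 is not unmonitored.** A reader might also infer that two DLTs could pass unnoticed. They should not, given the immediate telephone notice, the subject-level stop and continuous Sponsor review in a small open-label trial. What remains is narrower: noticing is provided for, but a hold and independent review are not required.

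**The 2-of-5 rule is not itself defective.** It is an escalation rule, and limiting it to cohort 1 fits a two-step design. Cohort 1 has no mid-cohort hold either, but it ends in a DMC review. The documents therefore do not support extending this point to cohort 1.

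**Few subjects benefit.** This stands. The larger figures need full stagger and rates of 30% to 60%, while the plan states no stagger and the fix imposes none. Cohort 2 also opens only after a DMC review. At a true cohort 1 rate of 50% or 60%, fewer than two DLTs in five has probability 1 − 0.813 = 0.19 or 1 − 0.913 = 0.09, so the high-rate figures matter mainly if toxicity rises steeply between the two doses. That gate is not absolute, however: two DLTs only lead the DMC to consider a reduction. If the 25% is taken off 350 mg/m², the result is 262.5 mg/m², still above 250.

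**Some reviews come too late to hold anything.** A(5) − A(4) is 0.029 at 10% and 0.082 at 20%, so about a third of triggered reviews would follow the last planned subject's DLT even under full stagger. Those reviews can still protect subjects on treatment.

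**Conclusion.** The point holds for the supplied synopsis. After cohort 2, or a repeated or reduced-dose cohort, opens, entry may continue after any number of DLTs without a required hold or independent review. This is more than missing detail, because the stated DMC remit leaves out conduct at the highest planned dose. The case for change rests on the required review, not on the number of subjects spared. The textual finding needs no assumption about rates; the probabilities rest on assumed DLT rates, independent subjects and five starts per cohort. Severity is low to moderate and confidence is moderate, because a rule may exist in documents not supplied.

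**What to change.** First check the protocol body and DMC charter. If they contain no such rule, add one for cohort 2 and for any repeated or reduced-dose cohort opened after cohort 1: when two subjects in that cohort have had a DLT, no new subject starts until the existing DMC has reviewed the safety data, including subjects still on treatment, and made a recommendation. Widen the DMC remit in Design and Methodology and in Data Analysis to match. Leave the cohort 1 escalation rule as it is.

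The hold acts when the second DLT is reported, so no waiting period between subjects is needed. The count prompts a review; it is not a tolerability criterion, and any dose consequence stays with the DMC and the Sponsor.

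The change costs a protocol amendment and matching charter wording. It uses the existing DLT definition, notification route and committee, with no new visit or sample. The operating cost is the occasional extra DMC review and pause in entry at tolerable DLT rates, as sized above.
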